1.5. Two-Week Adverse Event Phone Visit

The study team will call the participant two weeks after the baseline visit during each study period to administer an adverse events questionnaire and the Geriatric Depression Scale-15, and schedule the 4-week follow-up visit. To ensure ongoing consent, participants will be asked if they want to continue participation in the study. This visit is expected to take 15-30 minutes.

1.6. Four-Week Follow-Up Visit

Participants will be asked to fast for 10-12 hours, excluding water, the night before each four-week follow-up visit in order to collect fasting glucose as part of the CMP. A single blood sample (two teaspoons (10 ml)) and a urine sample will be collected to assess steady state plasma levels and excretion of WS compounds. Returned capsules will be counted to assess for adherence. Participants will have an ECG and blood and urine samples will be sent for safety labs (CBC, CMP, urinalysis, TSH, serum total testosterone, serum DHEA-S). The Geriatric Depression Scale-15 will be administered. At the four-week follow-up visit for the second study period, participants and investigators will be queried as to their perception of the dose sequence administered. This visit is expected to take 45-60 minutes.

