Safety, tolerability, and pharmacokinetics of an oral *Withania somnifera* product in older adults

NCT06171724

Version Date: 10.10.2024

Title: Safety, tolerability, and pharmacokinetics of an oral *Withania somnifera* product in older adults

Principal Investigator: [name], ND, MS [contact]

Co-Investigators/staff: [name] (Clinical Investigator) [contact]
[name] (Co-Investigator) [contact]
[name] (Study staff)
[name] (Study staff)

A. OBJECTIVES

A.1. Purpose

The purpose of this pilot study is to measure the oral absorption and pharmacokinetics (PK) of compounds from two doses of a standardized *Withania somnifera* extract product (Shoden®) in healthy older adults. Compound levels will be measured in human plasma and urine over 48 hours after acute oral administration and after four weeks' use of Shoden®. Peak exposure and time, total exposure, half-life, and urinary excretion of compounds will be calculated. These data will be used to inform decisions on the dosage and dosing frequency for future phase 1 and phase 2 clinical trials.

A.2. Primary goal

To determine the oral bioavailability and PK of withanolides from two doses of a *Withania somnifera* product (Shoden®) in healthy older adults following single administration and after four weeks' use.

A.3. Endpoints

- Primary endpoints:
 - Peak exposure and time (C_{max} , T_{max}) and total exposure (AUC_{0-t} , $AUC_{0-\infty}$) of withanolides from Shoden® in human plasma after a single administration.
- Secondary endpoints:
 - Half-life ($t_{1/2}$) of withanolides from Shoden® to help determine dosage intervals.
 - Urinary excretion of withanolides from Shoden®
 - Steady-state levels of withanolides after four weeks' use.
 - Tolerability and safety of Shoden® following single administration and after four weeks' use.
 - Feasibility of assessing sleep- and stress-related outcomes remotely using REDCap surveys.

B. SPECIFIC AIMS

Aim 1: Evaluate the oral absorption and PK of selected withanolides from Shoden® in older adults.

- **Hypothesis:** Selected withanolides will be detectable in the plasma and urine at both doses of Shoden®, with significantly greater plasma levels achieved at the 480 mg dose.

Aim 2: Assess the safety and tolerability of Shoden® in older adults.

- **Hypothesis:** A single administration and four weeks' use of Shoden® at 240 and 480 mg per day will be well tolerated and produce no severe adverse events.

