1.4.1. Baseline Visit (0-12hr)

Visit Timing: For the first study period, Baseline Visit 1 will occur a minimum of three days after the screening visit to allow for review of laboratory results and scheduling of appropriate facilities. For the second study period, Baseline Visit 2 will occur a minimum of two weeks (and not more than three weeks) after the four-week follow-up visit for the first study period.

Sample collection: Participants will be asked to fast for 10-12 hours, excluding water, the night before each baseline visit in an attempt to standardize gastrointestinal transit time and minimize delayed absorption of the study intervention due to the presence of food. Participants will be reminded during the pre-visit reminder call to arrive at the visit well-hydrated to facilitate blood collections. Study staff will place a peripheral intravenous catheter in the participant's arm or hand to allow for serial plasma specimen collection. Prior to administration of Shoden®, a baseline plasma sample of two teaspoons (10 ml) will be collected through the catheter using a syringe and transferred immediately into a heparinized Vacutainer tube. The participant will then be administered two capsules of Shoden® (240 or 480 mg total) on an empty stomach in the presence of study staff to ensure compliance. Participants will be asked to abstain from food and drink (excluding water) for the first two hours following consumption of Shoden® capsules to allow for transition into the small intestine and absorption. If signs of hypoglycemia are present, participants will be allowed to consume a high glycemic food and monitored for improvement. Participants will be provided water at the visit and will be encouraged to drink four 16-ounce cups of water over the 12 hours to maintain good hydration status. Serial blood samples (two teaspoons (10 ml) per sample) will be collected through a peripheral intravenous catheter, at 15, 30, 45, 60, 90, 120, 150, 180, 210, 240, 300, 360, 540, and 720 minutes after dosing. A baseline urine sample and a 12-hour pooled urine collection will be obtained to measure excretion of WS metabolites.

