Tolerability and safety: Participants' weight, height, body mass index, age, blood pressure, temperature, respiration rate, and pulse rate will be recorded at each study visit to monitor for adverse events and asymptomatic illnesses that may impact study results. Vitals will be collected at baseline, 7 hours post-Shoden administration, and at the end of each baseline visit. At the beginning of each baseline visit, participants will complete an electrocardiogram (ECG) and the Geriatric Depression Scale-15. Four teaspoons of blood (20 ml) will be collected for safety labs (CBC, CMP, urinalysis, TSH, serum total testosterone). ECG will be repeated 7 hours post-intervention to assess for cardiac changes. One teaspoon (5 ml) will be collected for a repeat CMP at 10 hours post-intervention to evaluate kidney and liver function. Participants will be interviewed and administered a standardized multi-system adverse events questionnaire at the beginning and end of each baseline visit. This visit is expected to take 13 hours a total of 175 mL of blood will be collected.

If the baseline CBC shows hemoglobin or hematocrit levels below what is recommended by the FDA for blood donation, the visit will be halted immediately. Participants will be asked to stay for 2.5 hours after the study agent has been administered to assess for acute side effects. Two and a half hours was chosen because common withanolides have reached their C_{MAX} by this time based on a previous PK study using Shoden®.⁸⁰ The end-of-visit adverse events questionnaire will be administered by phone and missed safety evaluations (7-hour ECG and vitals, 10-hour CMP, 12-hour vitals) will be collected at the 24-hour visit. After the 24-hour visit, the participant will be withdrawn from the study.

If study staff have difficulties collecting blood samples for any reason, the decision may be made to halt the visit. Participants will be asked to stay for 2.5 hours after the study agent has been administered to assess for acute side effects. If the visit ends before the 7-hour mark, the end-of-visit adverse events questionnaire will be administered by phone and missed safety evaluations (7-hour ECG and vitals, 10-hour CMP, 12-hour vitals) will be collected at the 24-hour visit. Participants will be allowed to remain on the study if difficulties with blood sample collection were the only reason for halting the study visit early.

I.4.2 24- and 48-Hour Visits

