Participants will return at 24 hours and 48 hours for a single blood collection (two teaspoons (10 ml)) and urine collection. Vitals will be collected. A CMP and ECG may be collected at the 24-hour visit if the baseline visit was halted prior to 7 hours. At the 48-hour visit, the adverse events questionnaire will be administered as the baseline measure for the subsequent four-week period. After the 48-hour visit, participants will be issued a 35-day supply of the appropriate dose of Shoden® (240 or 480 mg), which they will begin taking before bed every day for four weeks. These visits are expected to take 20 minutes. After analyzing the plasma and urine samples for the first two participants, a determination will be made as to whether the 48-hour PK visit is needed for future participants. If no withanolides are detected in plasma or urine at 48-hours, this time point will be eliminated to avoid undue participant burden.

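### The week-4 steady-state level rests on one sample per period whose time since the last dose is neither fixed nor recorded, and no steady-state parameter or analysis is defined for it

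*Combined protocol and SAP*

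**What the plan says.** Section A.2 gives the primary goal as "To determine the oral bioavailability and PK of withanolides from two doses" of the product, both after one administration and after four weeks of use. Section A.3 lists steady-state levels after four weeks as a secondary endpoint.

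The single-dose profile is tightly controlled. Under section I.4.1 the dose follows an overnight fast and is taken "on an empty stomach in the presence of study staff to ensure compliance". Blood is drawn "at 15, 30, 45, 60, 90, 120, 150, 180, 210, 240, 300, 360, 540, and 720 minutes after dosing", and section I.4.2 adds 24 h and 48 h.

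The four-week measure is specified differently:

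- **Dosing.** Participants receive a supply "which they will begin taking before bed every day for four weeks" (section I.4.2). The doses are unobserved and the hour is not set.
- **Sampling.** Section I.6 provides one draw: "A single blood sample (two teaspoons (10 ml)) and a urine sample will be collected to assess steady state plasma levels and excretion".
- **Timing.** "Participants will be asked to fast for 10-12 hours, excluding water, the night before each four-week follow-up visit". The stated reason for this fast is the glucose in the metabolic panel, not the pharmacokinetics.
- **Adherence.** "Returned capsules will be counted to assess for adherence". A count cannot date or time the last dose.

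Table 1 and the list of case report forms in section K.1 show no dosing log. Section L.1 applies paired tests to Cmax, the two AUCs and half-life, and a separate test to tmax. It names no trough, average or accumulation ratio and no comparison that uses the week-4 sample.

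**The concern.** One concentration means little without the time since the dose that produced it. The protocol expects early peaks: in the rule for halted visits it explains that "Two and a half hours was chosen because common withanolides have reached their" maximum by then, citing an earlier study of the same product. A draw the morning after a bedtime dose is therefore probably on the declining limb. It is neither a peak nor a 24 h trough. Where it falls on that limb depends on bedtime and appointment hour, and neither is captured.

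Two uses of the value are at stake. The first is judging accumulation by setting week 4 against the single-dose curve, which needs the elapsed time. The second is comparing 240 mg with 480 mg at week 4, where variation in timing adds to the variance. Elapsed time that is never recorded cannot be recovered by the analyst. Section A.1 says the data are meant to inform dosage and dosing frequency in later trials.

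**Working it through.** **Inputs from the documents.** n = 10 completers, d = 1.3, two-sided alpha 0.05, stated power 95% (L.4, L.1); once-daily dosing; peak by 2.5 h (I.4.1); a half dose expected to give Cmax 35–50% lower (L.4), so a full-to-half ratio of 1/(1 − 0.35) = 1.54 to 1/(1 − 0.50) = 2.0.

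**Assumptions, because the documents give no figures.** Half-lives of 2, 4, 8 and 12 h; mono-exponential decline after the peak; within-participant CV of 30% or 50%; SD of time since dose of 2 h.

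**Step 1: the plan's own figure.** Paired t-test, 9 degrees of freedom, noncentrality 1.3 × √10 = 4.11. Power is 0.954, so the stated 95% reproduces. L.4 frames it on Cmax, which comes from the single-dose profile. No figure is given for the week-4 sample.

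**Step 2: effect of timing against accumulation.** With half-life h, a timing difference of Δ hours changes concentration by 2^(Δ/h). The accumulation ratio under 24 h dosing is 1/(1 − 2^(−24/h)).

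| Half-life (assumed) | 2 h difference | 4 h difference | Accumulation ratio |
|---|---|---|---|
| 2 h | 2.0-fold | 4.0-fold | 1.00 |
| 4 h | 1.41-fold | 2.0-fold | 1.02 |
| 8 h | 1.19-fold | 1.41-fold | 1.14 |
| 12 h | 1.12-fold | 1.26-fold | 1.33 |

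A 2 h mismatch between the week-4 draw and the single-dose point it is set against exceeds the accumulation to be seen at half-lives of 2, 4 and 8 h. At 12 h the accumulation is larger than even a 4 h mismatch.

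**Step 3: precision of the dose comparison.** With k = ln 2/h, the SD of a participant's log ratio of 480 mg to 240 mg is √{2 × [ln(1 + CV²) + (k × 2)²]}.

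- Timing fixed, CV 30%: ln(1.09) = 0.0862, so SD = √(2 × 0.0862) = 0.415. The 95% confidence factor is exp(2.262 × 0.415/√10) = 1.35. Power for a true ratio of 2 (ln 2 = 0.693) is 0.997.
- Half-life 4 h, timing SD 2 h: k = 0.173 and (0.347)² = 0.120, so SD = √(2 × 0.206) = 0.642. The factor is exp(2.262 × 0.642/√10) = 1.58 and power is 0.86.

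| Timing | Power, CV 30% | Confidence factor, CV 30% | Power, CV 50% |
|---|---|---|---|
| Fixed | 0.997 | 1.35 | 0.83 |
| SD 2 h, half-life 2 h | 0.45 | 2.14 | 0.38 |
| SD 2 h, half-life 4 h | 0.86 | 1.58 | 0.66 |
| SD 2 h, half-life 8 h | 0.98 | 1.41 | 0.78 |
| SD 2 h, half-life 12 h | 0.99 | 1.38 | 0.81 |

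These use the top of the expected range, a ratio of 2. Power is lower at 1.54.

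**Step 4: detectability.** Relative to the 2 h concentration, the fraction left at x hours is 2^(−(x − 2)/h). At a 2 h half-life this is 12.5% at 8 h, 3.1% at 12 h and 0.8% at 16 h. Some week-4 values may therefore fall below quantification, and a log ratio would then be undefined.

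**The case against.** The strongest reply is that the trial is a randomised, double-blind crossover. Bedtime and appointment hour should not depend on which dose a participant is taking, so timing error widens the within-participant contrast without shifting it. That is right. A reader might infer that the doses cannot be compared at all at week 4, or that timing could systematically imitate a dose effect. The documents support neither reading, and at half-lives of 8 h or more the loss in Step 3 is small.

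Second, timing is not wholly uncontrolled. A bedtime dose and an overnight fast point to a draw the next morning, provided the last dose was taken the evening before. This also stands. The bound is loose, however, and no passage requires that last dose: participants hold a 35-day supply for four weeks of use, and nothing says what applies if the visit is late.

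Third, the plan promises levels, not an accumulation ratio, so the accumulation argument may seem aimed at an analysis nobody specified. This is partly right. The gap is better described as an undefined secondary endpoint. But a level called steady state, within a goal of pharmacokinetics after four weeks, invites the comparison, and randomisation does not protect it. If draws typically fall 2 h from the single-dose point used, the ratio is shifted, not merely noisy.

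Fourth, matching the time would not make the two occasions equivalent. Fed state, time of day and observation of dosing all differ. With 10 participants and a confidence factor of about 1.35, accumulation of 1.02 or 1.14 would not be resolved even with perfect timing. This stands and limits what the fix can claim.

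**Conclusion.** The point holds for the week-4 endpoint only. The interval from last dose to draw is loosely bounded, not fixed and not recorded, and L.1 gives no parameter or analysis for the sample. As written, the result cannot be located on the single-dose curve or used to judge accumulation.

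For the comparison between doses the consequence is lost precision. It ranges from severe at a half-life near 2 h (power 0.45 against 0.997, at CV 30% and timing SD 2 h) to slight at 8 h and above. All these sizes rest on assumed half-lives, CVs and timing spread. A reader might extend the criticism to the trial's main results. That does not follow: the primary single-dose endpoints come from observed, timed dosing, and the 95% power reproduces and is untouched.

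The case report forms themselves and the drawing in Figure 3 were not available for this check. A dose-time field or sampling window shown only there would narrow the point.

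**What to change.** Leave the dosing instruction as it is.

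1. At each week-4 visit, record the date and clock time of the last dose and of the blood draw. Ask at the visit itself, because a reminder call made beforehand would precede the bedtime dose.
2. Schedule the draw within a stated post-dose window that a morning visit allows and that matches an existing single-dose time, for example about 12 h (the 720-minute sample).
3. Define the endpoint as the week-4 concentration at that nominal time. Compare doses within participant on the log scale using actual elapsed time, with a stated rule for values below quantification.
4. Present any ratio of week 4 to single dose as descriptive. Say that fed state, time of day and observation of dosing differ, and that about 10 participants may not resolve small accumulation.
5. In A.2, limit only the part on four weeks of use to this concentration. The single-dose part stays.

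If the times are not recorded, report a week-4 spot concentration and drop the term steady state.

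The cost is a few form fields, a visit window and some wording in section L.1. The small downside is tighter scheduling of two visits per participant. Times not captured at the visit cannot be reliably reconstructed later, so this should be settled before further week-4 draws.
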